2.3 Exploratory Objectives, Other Assessments

- Biomarker specimens will be drawn at 4 time points prior to development of TMA. Values will be analyzed to determine whether any one biomarker or a combination of biomarkers may be predictive of TMA development or severity.

2.4 Endpoints

2.4.1 Primary Endpoints

- Incidence of missed doses of defibrotide
- Incidence of reportable SAE's
- Incidence of clinically significant bleeding requiring discontinuation of therapy
- Incidence of hypersensitivity reaction requiring discontinuation of therapy

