2.1 Primary

- To determine the safety and feasibility of administering prophylactic Defibrotide (provided by Jazz Pharmaceuticals) to a pilot population of patients at clinical high-risk for the development of severe TMA following HSCT. Safety to be determined with regard to bleeding risk and risk of hypersensitivity reaction. Feasibility to be determined with regard to administration concurrently with chemotherapy and supportive medications before, during, and after stem cell infusion

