5.1.1 Dose Modifications and Dosing Delays Tables for Specific Adverse Events

Adverse Event: Bleeding or Hypersensitivity reaction

Grade of Event	Management
≤ Grade 1	No change in dose
Grade 2	Hold until ≤ Grade 1 Resume at same dose level
Grade 3	Discontinue therapy
Grade 4	Discontinue therapy

*Patients requiring a delay of > 2 weeks should go off protocol therapy

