8.1 Study Endpoints

- Open label non-randomized un-blinded study to determine feasibility, safety, and efficacy.
- Feasibility endpoints;
 - Incidence of discontinuation of defibrotide. Study will be suspended if defibrotide is not tolerated as outlined below:

N (accrued)	0-6	7-12	13-18	19-24
Evaluate if discontinued in this many or more patients:	5	8	10	12

- Safety endpoints
 - Incidence of reportable SAE's (possibly drug-related and severe or unexpected). Study will be suspended if reportable AE's

N (accrued)	0-6	7-12	13-18	19-24
Evaluate if drug-related SAE's occur in this many or more patients:	4	7	10	12

- Incidence of TMA
 - Historical incidence: 7 of 22 (31.8%). With N=24, study will have 80% power to detect a statistically significant difference if incidence in this treated cohort is 8% or less.
 - Study will be re-evaluated if 2 patients develop TMA as this will render the secondary endpoint futile. May continue enrollment to determine feasibility and safety or expand the patient cohort.
- Incidence of Severe TMA
 - Historical incidence: 6 of 22 (27.3%). With N=24, study will have 70% power to detect a statistically significant difference if incidence in this treated cohort is 4% or less.
 - Study will be re-evaluated if 1 patient develops severe TMA as this will render the secondary endpoint futile. May continue enrollment to determine feasibility and safety or expand the patient cohort.

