8.4 Analyses Plans

8.4.1 Analysis Population

The analysis population will include all the patients who enroll that receive defibrotide.

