8.4.2 Primary Analysis (or Analysis of Primary Endpoints)

The primary efficacy analysis will be performed using the ITT population. The primary endpoint will assess the safety and feasibility of defibrotide. It will compare how many patients received the drug versus how many were intended to receive it. It will look into how many patients stopped the drug early and reasons for this.

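### The primary feasibility endpoint is missed doses, but the feasibility measures in section 8 count patients and do not register doses skipped or held when dosing resumes

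*Combined protocol and SAP*

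**What the plan says.** Section 2.1 sets the question: "Feasibility to be determined with regard to administration concurrently with chemotherapy and supportive medications before, during, and after stem cell infusion". Section 2.4.1 then lists "Incidence of missed doses of defibrotide" first among the primary endpoints. It does not say whether incidence is per dose or per patient, and no other section uses the term.

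Section 8 uses different measures:

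- Section 8.1 names the feasibility endpoint as "Incidence of discontinuation of defibrotide". Its monitoring row is headed "Evaluate if discontinued in this many or more patients", with limits of 5, 8, 10 and 12 patients for 0-6, 7-12, 13-18 and 19-24 accrued.
- Section 8.4.2 says of the primary endpoint: "It will compare how many patients received the drug versus how many were intended to receive it". It adds: "It will look into how many patients stopped the drug early and reasons for this".
- Section 8.4.1 defines the population: "The analysis population will include all the patients who enroll that receive defibrotide". Section 8.4.2 also mentions an ITT population and does not reconcile the two.

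On dosing, Table 5.1 gives a 2-hour infusion every 6 hours from the day before conditioning to Day +21, as an inpatient. The Abstract puts this at 28 to 35 days. Section 5.1.1 has a Grade 2 bleeding or hypersensitivity event held until it improves and then restarted at the same dose. Its footnote reads: "Patients requiring a delay of > 2 weeks should go off protocol therapy".

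**The concern.** The objective is about delivery: can four 2-hour infusions a day (8 hours of infusion time) be given alongside transplant chemotherapy and supportive drugs? Difficulty of that kind can show as doses skipped or delayed while the patient stays on treatment. The 2.4.1 endpoint would capture it. The section 8 measures would not, because each asks only whether a patient started or permanently stopped.

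An analyst who follows section 8 could therefore report full feasibility when a material share of the planned drug was never given. Any missed-dose figure reported alongside would rest on a definition chosen after the data were in hand, in a pilot whose main purpose is feasibility.

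**Working it through.** The plan states no missed-dose rate, threshold or precision, so there is no figure to reproduce. The check asks what each section 8 measure records under dosing patterns that the plan allows or does not rule out.

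**Inputs**

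- Interval of 6 hours (Table 5.1): 24 / 6 = 4 doses a day.
- Course of 28 to 35 days (Abstract): 4 × 28 = 112 to 4 × 35 = 140 planned doses.
- Grade 2 events are held and then restarted; a delay of more than 2 weeks takes the patient off therapy (5.1.1).

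**Formulas**

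- Share missed through daily skips = doses skipped per day / 4.
- Share missed through a hold = (4 × days held) / planned doses, if held doses are not made up.

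**Results for one patient and one course**

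| Pattern | Doses missed | Share of course | Received drug (8.4.2) | Discontinued (8.1) | Stopped early (8.4.2) |
|---|---|---|---|---|---|
| One dose skipped every day | 28 of 112 to 35 of 140 | 25% | Yes | No | No |
| 3-day hold, then restart | 12 | 12/140 = 9% to 12/112 = 11% | Yes | No | No |
| 7-day hold, then restart | 28 | 28/140 = 20% to 28/112 = 25% | Yes | No | No |

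The last three columns match those of a patient who received every dose. Such a patient adds nothing to the 8.1 count, so the limits of 5, 8, 10 and 12 cannot respond to these patterns however common they are.

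**The received-versus-intended comparison.** If the 8.4.1 population applies, everyone in it has received defibrotide and the comparison is 100% by construction. If ITT in 8.4.2 means all enrolled patients, the comparison finds patients who were never dosed. Neither reading reaches individual doses.

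**Make-up dosing.** Section 3.4 qualifies the Day +21 end by reference to delays from adverse events, which could be read as letting held days be made up. Tables 5.1 and 6.1 end dosing at Day +21, and no make-up rule is given. If make-up is intended, the hold rows shrink. The skipped-dose row does not, since 3.4 speaks only of adverse-event delays.

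**The case against.** The best defence is that 2.4.1 already names the endpoint as primary. In a single-arm pilot with no test on it, incidence is a descriptive count that the team would tabulate anyway. The Abstract plans weekly inpatient assessments of administration feasibility, and 8.2.2 treats failure of feasibility as its own reason for leaving the study. The 8.1 row is a sensible tolerability monitor, and 8.4.2 reports early stops with reasons.

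Much of this stands, and it limits the point. A reader might infer that missed doses will go unreported. The documents do not support that: 2.4.1 still obliges some report, and section 8 does not withdraw it. But section 8 does more than stay silent. It names a different feasibility endpoint and describes a primary analysis made of patient counts. The weekly assessment does not fill the gap, because neither the treatment-period list in 6.1.2 nor Table 6.1 has an item for it.

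A reader might also infer that up to half of the planned drug is likely to be lost. A single 14-day hold, the longest before a patient leaves therapy, would be 56 doses, or 40% of 140 to 50% of 112. That is a limit of the rule. It needs a Grade 2 bleeding or hypersensitivity event lasting two weeks, with no make-up. The documents give no rate of holds, skipped doses or early discharge, so no expected loss can be derived.

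**Conclusion.** The point holds as a mismatch between endpoint and analysis. The first primary endpoint concerns doses, while the feasibility measures in section 8 concern patients, and they miss any dose skipped or held before a restart. The illustrative size is 25% of a course for one skipped dose a day and 20-25% for a 7-day hold, both with perfect section 8 counts. The hold figure assumes no make-up after Day +21; the daily-skip figure does not depend on that or on course length. Both are examples of what could go unseen. Nothing in the documents shows that feasibility will in fact be overstated. The issue is moderate and worth correcting because the remedy is cheap and answers the 2.1 question directly.

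**What to change.** Align 8.1 and 8.4.2 with 2.4.1 by making the primary feasibility analysis doses given / doses planned, per patient and pooled, for each transplant course. Tandem patients repeat the schedule, so each course needs its own denominator. Specify:

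- **Planned doses:** every 6 hours from the actual first scheduled dose (9 pm ± 3 hours on the day before conditioning, per 6.1.2.1) through Day +21, ending earlier at death, progression or withdrawal. Counting from the first scheduled dose avoids scoring doses before the evening start as missed.
- **Missed dose:** one not started before the next scheduled dose, or not completed. This settles late and partial infusions.
- **Reason for each missed dose:** toxicity hold or stop; conflict with chemotherapy or supportive drugs; discharge; other.
- **Reporting:** show misses from toxicity and from administration conflict separately from those due to discharge, so that well patients sent home early do not look like delivery failures. List enrolled patients who were never dosed.

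Keep the 8.1 discontinuation row as a tolerability monitor. A count of patients reaching a pre-set share of planned doses, for example 80%, is optional and the threshold is the team's choice.

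The cost is a missed-dose count and reason on the case report form, covering 24 × 112 = 2,688 to 24 × 140 = 3,360 planned doses for 24 single-course patients, and more with tandem courses. Section 9.5 already requires dispensation records. No patients, visits, samples or regimen changes are added.

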2.4.2 Secondary Endpoints

- Incidence of TMA as diagnosed by criteria listed in section 7.2.1.
- Incidence of severe TMA as diagnosed by criteria listed in 7.2.2.

2.4.3 Exploratory Endpoints

- Incidence of elevation of single or combination of biomarkers predictive of development of TMA

3 Study Design

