1.4 Correlative Studies

Biomarkers indicative of endothelial damage and TMA activity will be drawn to assess subclinical TMA activity as well as risk for subsequent development of TMA while on defibrotide. These include plasma free hemoglobin (UCSF clinical lab), suppression of tumorigenicity (ST2, Viracor), angiotensin 2 (Ang2, Myriad), and plasminogen activator inhibitor – 1 (PAI-1, Quest). Study labs will be assessed at 4 time points prior to Day +21, and at diagnosis of TMA.

Hypothesis:

1. The incidence of TMA will correlate with increases in one or more of these biomarkers over baseline at any time post-HSCT.
2. The severity of TMA will correlate with a maximum increase in one or more of these biomarkers.

This will provide a predictive basis for future patients who may require preemptive treatment of early / preclinical TMA.

2 Objectives of the Study

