6.1.4 Discontinuation of Therapy

The Investigator will withdraw a patient whenever continued participation is no longer in the patient's best interests. Reasons for withdrawing a patient include, but are not limited to, disease progression, the occurrence of an adverse event or a concurrent illness, a patient's request to end participation, a patient's non-compliance or simply significant uncertainty on the part of the Investigator that continued participation is prudent. There may also be administrative reasons to terminate participation, such as concern about a patient's compliance with the prescribed treatment regimen

Table 6.1: Schedule of Study Procedures and Assessments⁴

	Screen	Days Pre-HSCT			Days Post-HSCT				Weeks Post-HSCT					TMA Dx
(+/- in days)	Admit (-28)	Admit	-7 (+/- 2)	-1 (+/- 1)	7 (+/- 2)	14 (+/- 2)	21 (+/- 2)	28 (+/- 2)	8 (+/- 7)	12 (+/- 7)	16 (+/- 7)	20 (+/- 7)	24 (+/- 7)	Dx (+/- 3)
Informed consent	X													
AE assessment		X	X	X	X	X	X	X	X	X	X	X	X	X
Defibrotide		X	X	X	X	X	X							+/-
Physical exam *		X	X	X	X	X	X	X	X	X	X	X	X	X
Vital signs *		X	X	X	X	X	X	X	X	X	X	X	X	X
Medical History *		X	X	X	X	X	X	X	X	X	X	X	X	X
Standard Labs ¹ *		X	X	X	X	X	X	X	X	X	X	X	X	X
Study Labs ²		X³		X	X		X							X

1. Labs per standard of care should include CBC, complete chemistry, LDH, uric acid, haptoglobin, direct antiglobulin test, peripheral smear for RBC morphology, urine protein concentration, urine protein / creatinine ratio, CH50, coagulation panel.
 2. Study labs to include plasma free Hgb, ST2, Ang-2, PAI-1, and hold specimen.
 3. +/- 2 day window
 4. Patients undergoing tandem autologous transplants will repeat the schedule of procedures and assessments on admission for second transplant, with the exception of screening.
- * Standard of care for patients undergoing HSCT

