8.2 Determination of Sample Size and Accrual Rate

Based on historical controls, we estimate accrual of 12 patients per year, with a goal of 24 patients by 2 years.

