8.4.4 Other analyses/Assessments

Other analysis include incidence of TMA by Day +30 post-HSCT, non-relapse mortality by Day +100 and by Day +180 post-HSCT. Summaries for biomarkers will be provided. Additional exploratory analyses may be performed based on incidence of elevation of single or combination of biomarkers predictive of development of TMA.

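### The biomarker endpoint is worded as a yes/no elevation with no threshold, which does not match the plan's own aim of analysing values and, if followed, would discard information with only about 2 to 8 TMA cases

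*Combined protocol and SAP*

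**What the plan says.** Four assays are planned (Table 6.1, footnote 2): "Study labs to include plasma free Hgb, ST2, Ang-2, PAI-1, and hold specimen". Table 6.1 schedules draws at admission, Day -1, Day +7, Day +21 and at TMA diagnosis.

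The plan describes the use of these measurements in four places:

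- Section 1.4, hypothesis 1: "The incidence of TMA will correlate with increases in one or more of these biomarkers over baseline at any time post-HSCT".
- Section 1.4, hypothesis 2: "The severity of TMA will correlate with a maximum increase in one or more of these biomarkers".
- Section 2.3, objective: "Values will be analyzed to determine whether any one biomarker or a combination of biomarkers may be predictive of TMA development or severity".
- Section 2.4.3, endpoint: "Incidence of elevation of single or combination of biomarkers predictive of development of TMA".

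In the analysis plan, section 8.4.4 says "Summaries for biomarkers will be provided" and then "Additional exploratory analyses may be performed based on incidence of elevation of single or combination of biomarkers predictive of development of TMA". No section gives a threshold for elevation, a rule for combining markers, a test, or a power figure for the biomarker question.

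**The concern.** Plasma free hemoglobin, ST2, Ang-2 and PAI-1 are measured on continuous scales. An incidence of elevation turns each into a yes/no count, so a patient just over the cut and one far above it contribute the same. The two sections an analyst would work from, the endpoint and the analysis plan, use the yes/no form. The objective speaks of values and hypothesis 2 of the size of the increase.

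Two things are at stake. First, TMA cases will be few, so information lost to a cut cannot be recovered. Second, with no threshold fixed, a cut could be chosen after the results are seen. Section 1.4 intends this work as a predictive basis for preemptive treatment of future patients, so the analysis variable should be settled beforehand.

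**Working it through.** **No stated figure to reproduce.** The documents give no power, effect size, SD or cut for the biomarkers. Everything below on power is conditional on assumptions, which are named.

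**Expected number of TMA cases.** Section 8.2 sets N = 24 ("with a goal of 24 patients by 2 years"). Section 8.1 gives a historical TMA rate of 7/22 and a target of 8% or less.

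- At the target: 24 × 0.08 = 1.9, about 2 cases.
- At the historical rate: 24 × 7/22 = 7.6, about 8 cases.
- Severe TMA: 24 × 0.04 = 1.0 to 24 × 6/22 = 6.5 cases.

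**What a cut can show with 2 cases.** If both cases are elevated and k of all 24 patients are elevated, the Fisher p-value for k = 5 or 6 is C(k,2)/C(24,2).

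- k = 5: 10/276 = 0.036.
- k = 6: 15/276 = 0.054.

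So p ≤ 0.05 requires that no more than 5 of the 24 patients are elevated, including both cases. This needs no effect-size assumption.

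**Power, values against a cut.** Assumptions: log-scale values are normal with equal SD, TMA cases are shifted up by d SD, and tests are two-sided at 5%. (The plan states alpha only for severe TMA, without sidedness.) Values are compared by exact Wilcoxon, simulated with 40,000 runs. For the cut, Fisher power is the sum of binomial probabilities over all tables with p ≤ 0.05. The cut is the best of four, at the 50th, 75th, 90th and 95th percentile of non-cases.

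Worked example with 2 cases, d = 1.0 and a cut at the 90th percentile:

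- P(a case is elevated) = 1 − Φ(1.282 − 1.0) = 0.389, so both are elevated with probability 0.151.
- At most 3 of 22 non-cases may be elevated: P(Bin(22, 0.1) ≤ 3) = 0.828.
- Power = 0.151 × 0.828 = 12.5%.

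Power in %, Wilcoxon / best Fisher cut (gap in points):

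| Shift d | 2 cases | 4 cases | 8 cases |
|---|---|---|---|
| 0.5 | 8.3 / 3.9 (4.4) | 12.4 / 7.3 (5.1) | 17.6 / 9.9 (7.7) |
| 1.0 | 21.4 / 12.5 (8.9) | 36.7 / 22.3 (14.4) | 55.1 / 34.8 (20.3) |
| 1.5 | 42.0 / 28.5 (13.5) | 68.3 / 45.3 (23.0) | 88.3 / 68.3 (20.0) |

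Because Fisher's test is discrete, case counts in between move the gap by a few points: about 3 points with 5 cases at d = 0.5, and about 26 with 7 cases at d = 1.2. With 8 cases the gap narrows again at very large shifts, to about 9 points at d = 2.0.

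**How much is Fisher's conservatism?** With no shift at all, the best-cut Fisher test rejects about 1% of the time with 2 cases and about 2% with 8 (75th-percentile cut). The exact Wilcoxon rejects about 4% to 5%. A comparison at equal nominal level uses the normal approximation, power = Φ(d·√(m(24−m)/24) − 1.96) for m cases, with d multiplied by √(2/π) = 0.798 for a median split. At d = 1.0:

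- m = 2: 27.2% against 19.0%, a loss of 8.3 points before rounding.
- m = 4: 44.7% against 30.7%, a loss of 13.9 points.
- m = 8: 63.7% against 45.3%, a loss of 18.3 points.

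At d = 0.5 the loss is 2.2 points (m = 2) to 6.1 points (m = 8). The approximation is rough with 2 cases, and the median split is only a convenient reference. It shows that a loss remains without Fisher's test.

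**The case against.** The strongest reply is that the plan does not commit to a yes/no analysis. Section 2.3 says values will be analysed, 8.4.4 promises biomarker summaries, and the analysis based on elevation is optional. This stands. A reader might infer that the trial will reduce its four assays to binary data and nothing else. The documents do not support that. What they show is an endpoint and an analysis section that do not match the objective and hypothesis 2, with no method named to settle it. The objective in 2.3 supports the proposed fix.

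A reader might also infer that a yes/no analysis could not address the hypotheses in 1.4. That goes too far. Hypothesis 1 concerns increases over baseline, and a yes/no increase fits it. Only hypothesis 2 is clearly about size.

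It is also fair to say that the power loss is not a property of the plan. It depends on an assumed shift and cut, and part of it comes from Fisher's test, which the plan does not name. A median split, or a cut picked to give the smallest p-value, would perform badly, but the plan proposes neither.

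Finally, eight cases is the upper end. Section 7.1 pauses the study once TMA cases exceed 2, and 8.1 re-evaluates it at 2, although enrolment may continue. With 2 cases and a 1 SD shift, even the measured values give only about 21% power. That limits the practical gain but does not justify the mismatch.

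**Conclusion.** The point holds as a misalignment and a missing definition. Sections 2.4.3 and 8.4.4 name a yes/no variable without a threshold, while 2.3 and hypothesis 2 of 1.4 call for values and the size of the increase. Following the endpoint as worded would discard information in a study expecting about 2 to 8 TMA cases.

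The size is conditional. Under normal log-scale values, N = 24 and the best of four fixed cuts, with 2, 4 or 8 cases, the loss is about 4 to 8 points for a 0.5 SD shift and about 9 to 23 points for 1.0 to 1.5 SD, part of it due to Fisher's conservatism. It would be wrong to read any single loss figure as following from the documents. Because the analysis is exploratory and optional in a safety and feasibility pilot, this is an inexpensive improvement and does not threaten the trial's primary conclusions.

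**What to change.** In 2.4.3 and 8.4.4, replace the yes/no variable as follows:

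- **Variable.** For each marker, use the maximum log ratio to the admission baseline over scheduled draws taken before TMA diagnosis. Apply the same draw window to patients without TMA, since a maximum over more draws tends to be larger. Write the window down in advance. It matters because section 1.3 reports some TMA within a week of transplant, so the Day +7 and +21 samples may follow onset. Tandem patients repeat the schedule, so state which transplant supplies their values.
- **Analysis.** Compare patients with and without TMA by exact Wilcoxon and report the AUC with a 95% CI. Show values by TMA severity descriptively, because 1 to 6.5 expected severe cases will not carry a test.
- **Multiplicity.** Use one summary per marker and label the four comparisons exploratory and unadjusted. If independent, four tests at 5% carry a 1 − 0.95^4 = 18.5% chance of at least one false positive. Testing each marker separately at Day -1, +7 and +21 would make 12 tests and 1 − 0.95^12 = 46%.
- **Elevation.** Keep the incidence of values above the laboratory's upper limit as a descriptive summary only, with no cut chosen from the trial data.

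The cost is a few sentences of wording. The draws and assays are already scheduled, so no extra samples or patients are needed. The downside is that a rank or AUC result does not itself give a clinical threshold, which a later study would have to set.
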